
**Sample Size Requirements and Power Calculations.** Current available literature suggests that at least 20% of the symptomatic COVID-19 infected population may develop frailty, organ dysfunction or death within one year(46, 47, 52, 56, 57, 61, 62, 113-116). Based on these assumptions, we will perform power calculations on the following numbers (250 civilians, 250 Veterans) (**Figure 2**): Aim 1.1 single-omic identification (n=100, 80 endpoint negative/20 endpoint positive) and confirmation (n=200, 160 endpoint negative/40 endpoint positive) of candidate genomic, transcriptomic, proteomic and clinical parameters that correlate with outcomes; Aim 1.2 multi-omics correlation analysis (n=300 from Aim 1.1, 240 endpoint negative/60 endpoint positive); Aim 1.3 WGCNA and pathway analysis (n=300 from Aim 1.1); Aim 2.1 training/testing of the predictive algorithm (n=300 from Aim 1.1); Aim 2.2 independent validation of predictive algorithm (independent n=200). Samples will be processed in 5 batches, approximately 120 samples per year within 5 years. Statistical analysis will begin after one-year outcomes of the first 100 patients have been collected. Patients will be stratified by outcomes, Veteran/civilian status, age, gender, ethnicity, comorbidities, frailty and other parameters that appear to be significant such as alcoholism.

**Timeline.** The timeline of the entire project is summarized in **Table 3**. We anticipate that: 1) recruitment of 600 COVID-19 patients will be begin 3 months after funding start, be completed within 42 months, 2) the 12-month follow-up period will be completed by month 57, and 3) the analysis will be completed by month 60.

Immune Cell Subsets	
Cell Population	Phenotype
T cells	CD3+CD4+ or CD3+CD8+
Naive	CCR7+CD45RA+
Effector Memory	CCR7-CD45RA-
Central Memory	CCR7+CD45RA-
TEMRA	CCR7-CD45RA+
Activated Effector	CD25++CD127hi
Regulatory	CD4+CD25++CD127lo
Antigen-experienced	KLRG1+
Limited capacity memory	CD38+
Chronically activated	CD57+
Activated suppressive	PD1+
Natural Killer Cells	CD3-CD56+
Cytotoxic	CD56dimCD16+
Cytokine producing	CD56brightCD16+
B Cells	CD19+
Transitional	CD38++CD24+
Mature Naive	CD27-IgD+
Memory	CD27+
Non-Switched memory	CD27+IgD-
Switched Memory	CD27-IgD+
Plasmablasts	CD27+CD38++
Regulatory	CD5+CD24+

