## **AIM 2: TRAIN AND VALIDATE ALGORITHM FOR OUTCOME PREDICTION**

**Hypothesis and Objectives.** We hypothesize that our algorithm will predict COVID-19 short- and long-term outcomes more accurately than clinical parameters alone. Our objectives are to train the algorithm in a mixed US-high risk COVID-19 population (Aim 2.1) and validate the predictive algorithm on an independent mixed US-high risk COVID-19 population (Aim 2.2).

**Aim 2.1: Train algorithm for outcome prediction. Objective.** Our objective is to train and test our algorithm in a mixed US COVID-19 population, which will improve prediction of adverse short- and long-term outcomes(92, 173). **Bioinformatics. Parameter Selection.** Model development will largely follow the modeling reported in the preliminary data section and will be constructed using significant entities identified in the marker screening phase (Aim 1). Since VA and civilian patients may have different co-morbidity and risk profiles, these models will also include a term for whether the patient is from the VA or civilian setting. This term, if significant, will allow flexibility in our models to make different predictions based upon known characteristic differences between VA and civilian patient populations. **Power calculations.** The first 300 samples (240 endpoint negative and 60 endpoint positive)

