will be used for model building (**Figure 2**). The overall sample size will support the following: 1) This sample size will be sufficient to include approximately 10 clinical features based on conventional rules of thumb suggesting that we should have 10-15 subjects in the less frequent outcome category per variable in a logistic regression model; 2) This will allow us to estimate the AUC for the model with a precision of approximately 0.032 (based on the 95% confidence interval for the AUC and an overall AUC of at least 0.8); 3) Provide 80% power for detecting delta AUCs between pairs of models (see below) of 0.1 assuming that the models will have a correlation of 0.5 and AUCs of ~0.8. **Logistic regression modeling. Logistic regression modeling.** We will assess the algorithm by constructing three separate logistic regression models, one using clinical factors alone as our baseline model, one using clinical factors plus the significant omics markers from the screening phase (genomics, transcriptomics, and proteomics parameters), and one using clinical factors plus a simplified list of significant omics features (e.g. bedside, rapid test, easy to obtain). Each of the three models will have variable selection and coefficients estimated by the LASSO method and validation results and comparisons between the three models performance (AUC) will be validated in Aim 2.2. **Model building optimization by cross-validation.** Ten-fold cross-validation will be used to estimate model performance in terms of AUC. The AUCs will be compared between models with DeLong's test for paired AUCs. **Interpretation of Results.** We expect to derive a multi-omics algorithm that will predict outcomes of COVID-19 patients more accurately than clinical data alone.

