**Aim 2.2: Independently validate predictive algorithm for outcome prediction. Objective.** Our objective is to validate the algorithm in an independent randomly selected mixed US COVID-19 population who were not used for algorithm development(173). **Bioinformatics.** We will validate the performance of the prototype test algorithm to predict the composite endpoints in an independent cohort of 200 patients (**Figure 2**). Rigorous testing of the analytical performance of the test will identify and quantify the technical variations of the test performed on the patient samples and will be done in a blinded fashion, without knowledge of the clinical status or treatment outcomes of the patients whose data was obtained. For model testing, the sample size of 200 (160 endpoint negative and 40 endpoint positive) will provide precision of +/- 0.066 for the testing AUC as well as an 80% power to detect differences in AUCs between models of 0.12, when comparing models based on clinical features alone and models combining clinical and molecular features. Finally, with this sample size we will be able to estimate the precision of the sensitivity and specificity (based on the width of the 95% confidence intervals) between 0.0545 to 0.11 depending on the observed values of those performance characteristics. *We plan to make the raw data and the algorithm publically available as a web-based free tool for further scientific development by the international scientific community.* **Interpretation of Results.** We expect that the algorithm will confirm the desired clinical test performance, i.e. increase accuracy of one-year primary endpoint (new onset or worsening frailty, organ dysfunction or death) prediction of at least AUC 0.12.

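### The AUC precision of about 0.032 claimed for the 300 training samples is not a 95% half-width at AUC 0.8, and it does not fit the ±0.066 claimed for validation

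*Protocol*

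**What the plan says.** In the protocol, the power calculations under Aim 2.1 take "The first 300 samples (240 endpoint negative and 60 endpoint positive") as the model-building set. The second of three numbered statements about what this sample supports reads "This will allow us to estimate the AUC for the model with a precision of approximately 0.032", with the condition "based on the 95% confidence interval for the AUC and an overall AUC of at least 0.8". The third concerns differences in AUC between models and is calculated "assuming that the models will have a correlation of 0.5 and AUCs of ~0.8".

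Under Aim 2.2, the protocol says that "the sample size of 200 (160 endpoint negative and 40 endpoint positive) will provide precision of +/- 0.066 for the testing AUC". No AUC is attached to that figure. Neither place names a variance formula, and neither says which outcome class scores higher. The split into events and non-events in both cohorts follows from the assumption, under Sample Size Requirements and Power Calculations, that "at least 20% of the symptomatic COVID-19 infected population may develop frailty, organ dysfunction or death within one year".

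**The concern.** The training figure comes with its conditions: confidence level, class counts and a floor for the AUC. It can therefore be checked, and 60 events look too few for so narrow an interval. The two precision figures also look odd side by side. The cohorts share the same event rate and differ only by 300 against 200 patients, yet the second figure is about double the first.

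AUC is the study's measure of performance. A reader who takes 0.032 at face value would expect an observed training AUC of 0.80 to carry an interval of about 0.77 to 0.83. If the interval is really about twice as wide, the training result is much less firm than the text suggests. That bears on how it is read beside the AUC gain of 0.12 that Aim 2.2 expects.

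**Working it through.** **Inputs.** Training: 60 events, 240 non-events (Aim 2.1). Validation: 40 events, 160 non-events (Aim 2.2). AUC: A = 0.80, the least favourable value allowed by "an overall AUC of at least 0.8". Confidence: 95%, z = 1.96. The formula is not given, so several are tried. All treat the score as fixed.

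**1. Hanley-McNeil, events as the positive class.** With m positives and n negatives,

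Var(A) = [A(1−A) + (m−1)(q₁−A²) + (n−1)(q₂−A²)] / (mn), where q₁ = A/(2−A) and q₂ = 2A²/(1+A).

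At A = 0.80, q₁ = 0.6667, q₂ = 0.7111 and A² = 0.64. For m = 60 and n = 240:

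- numerator = 0.16 + 59 × 0.02667 + 239 × 0.07111 = 0.160 + 1.573 + 16.996 = 18.729
- variance = 18.729 / 14,400 = 0.001301; SE = 0.0361
- half-width = 1.96 × 0.0361 = **0.071**

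**2. Other formulas for the same 60/240 at AUC 0.80.**

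| Formula | SE | 95% half-width | Ratio to 0.032 |
|---|---|---|---|
| Hanley-McNeil, classes swapped (m = 240, n = 60) | 0.0273 | 0.0535 | 1.7 |
| Equal-variance binormal | 0.0314 | 0.0616 (simulation 0.0613) | 1.9 |
| Hanley-McNeil, events positive | 0.0361 | 0.0707 | 2.2 |
| Obuchowski binormal approximation | 0.0376 | 0.0738 | 2.3 |

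A logit-scale interval with the Hanley-McNeil SE gives 0.0708. None of these reproduces 0.032 as a half-width. Read as a full width, 0.032 is further off: the smallest full width in the table is 2 × 0.0535 = 0.107.

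**3. Other ways to reach 0.032.**

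- *A higher AUC.* At AUC 0.90, Hanley-McNeil gives 0.054, or 0.035 with classes swapped. A half-width of 0.032 needs an AUC of about 0.967 (Hanley-McNeil), 0.938 (binormal) or 0.913 (Hanley-McNeil, swapped).
- *All 500 completers.* At AUC 0.80 with 100/400, Hanley-McNeil gives 0.055, or 0.041 swapped.
- *One standard error.* The SE for 60/240 is 0.0314 (binormal, AUC 0.80), 0.0327 (Obuchowski swapped, AUC 0.80) or 0.0324 (Hanley-McNeil, AUC 0.85). This is the closest match.

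**4. Consistency of the two stated figures.** At the same AUC, formula and 20% event rate, half-widths scale nearly as 1/√n.

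- Expected ratio, validation to training: √(300/200) = 1.22
- Stated ratio: 0.066 / 0.032 = 2.06
- ±0.066 scaled to 300 patients: 0.066 / 1.22 = 0.054

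**5. The ±0.066 (40/160).**

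- AUC 0.80, events positive: 0.0866 (Hanley-McNeil), 0.0904 (Obuchowski), 0.0755 (binormal)
- AUC 0.80, Hanley-McNeil, classes swapped: 0.0656
- AUC 0.90, Hanley-McNeil: 0.0657
- AUC 0.85, binormal: 0.0653

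The last three agree, or nearly agree, with the stated figure.

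**The case against.** The strongest reply is that the protocol names no formula, so no single number can be called the correct half-width. That stands. The value 0.071 is one formula with one class orientation, and the figures at AUC 0.80 run from 0.054 to 0.074. But the whole range lies well above 0.032, so the choice of formula does not rescue the claim. The wording of at least 0.8 does not rescue it either: a precision promised for any AUC from 0.8 upward has to hold at 0.8.

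A second reply is that the factor of 2.06 is a contradiction only if both figures rest on the same AUC and formula, which Aim 2.2 does not say. This is fair. The mismatch supports the point but does not prove it, and the error in Aim 2.1 does not depend on it.

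A reader might go further and infer that ±0.066 is wrong as well and must become ±0.087. The protocol does not support this. It attaches no AUC to that figure. An AUC of 0.90 is what one preliminary model with genes and clinical data reached (Preliminary Data, Study 1). The swapped orientation also has a basis: in that study higher scores predict survival, and Aim 2.1 says model development will largely follow that work. The figure is under-specified, not refuted.

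Nor is it shown that 0.032 is a standard error reported by mistake. The size fits, but the protocol does not say how the figure was obtained.

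Finally, the consequence is limited. The cohort sizes are fixed first and the calculations made on them, no test or decision rule uses 0.032, and performance is judged in the independent 200.

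**Conclusion.** The figure of 0.032 is wrong as written. For 60 events and 240 non-events at AUC 0.8, the 95% half-width is about 0.05 to 0.07 depending on the formula, and 0.071 by Hanley-McNeil with events as the positive class. The claim is too optimistic by a factor of at least 1.7. Around an AUC of 0.80 the design gives an interval of about 0.73 to 0.87 (Hanley-McNeil), or 0.75 to 0.85 on the most favourable formula tried.

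The two stated precisions cannot both hold under one AUC, one formula and one meaning of precision. On a common basis, ±0.066 in validation implies about 0.054 in training.

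These results assume the planned 20% event rate, a 95% two-sided interval and a score treated as fixed. The point is an error in a stated justification and is moderate in weight. It does not show that the training cohort is too small for its purpose.

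**What to change.** In Aim 2.1, replace 0.032 with a 95% half-width of about 0.07 (Hanley-McNeil, AUC 0.8, 60 events and 240 non-events), noting that usual formulas range from about 0.05 to 0.07.

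In both Aim 2.1 and Aim 2.2, state the formula, the assumed AUC, which class scores higher, and that the figure is a half-width. Use the same choices in both places. If AUC 0.8 with events as the positive class is meant throughout, the validation figure becomes about 0.087 by Hanley-McNeil (about 0.076 binormal). If ±0.066 is kept, state the assumptions that produce it and recompute the training figure on them. For example, AUC 0.80 by Hanley-McNeil with event-free patients scoring higher gives 0.066 and 0.054.

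The cost is a few words and one or two numbers. No patients are added and no analysis changes.

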## SPECIFIC AIMS

**AIM 1: CORRELATE MULTIOMIC DATA WITH OUTCOMES. Hypothesis and Objectives.** We hypothesize that various clinical COVID-19 disease outcome phenotypes correlate with molecular data and clinical patterns and are associated with immunologic pathways. Our first objective is to identify and confirm mono-dimensional genomic, transcriptomic, proteomic and clinical parameters that correlate with outcomes (Aim 1.1). Outcomes are defined as new onset or worsening frailty, single organ dysfunction, multiorgan dysfunction, and death within one year (primary endpoint) and at time of discharge (secondary endpoint). Since genomics, transcriptomics and proteomics often have complementary roles, our second objective is to perform multi-omics correlation analysis (Aim 1.2). Our third objective is to perform Weighted Gene Co-Expression Network Analysis (WGCNA) and pathway analysis to understand the role of the genes involved in the inflammatory response during SARS-CoV-2 infection (Aim 1.3).

**Aim 1.1: Single-omic identification of candidate genomic, transcriptomic, proteomic and clinical parameters that correlate with outcomes. Objective.** Our objective is to identify single-omic parameters (genomic, transcriptomic, proteomic) and clinical data that correlate with COVID-19 outcomes. We will perform exploratory analyses on the first 100 samples and confirm these parameters on the following 200 samples (**Figure 2**). **Genomic Analysis.** Raw cfDNA sequences will be aligned to HG38 and cf-mtDNA to HG38\_MT\_only (Strand NGS 3.3.1). ComBat will be used for batch effect correction(164-166). We will calculate the number of cf-mtDNA fragments in each sample. **Transcriptomic Analysis.** Raw transcriptome data will be aligned (HG19) and normalized (DESeq), batch effect corrected by ComBat(164-166) and filtered by expression (20th to 100th percentile) (Strand NGS (Avadis)). Differentially expressed genes between positive and negative endpoint groups will be identified by non-parametric statistics (Mann-Whitney test with Benjamini-Hochberg correction). We will use a more relaxed criteria of FDR=0.1 and fold change of at least 2.0 to identify significant genes as previously described by our group(90, 167, 168). **Immunophenotyping Analysis.** We will identify COVID-19

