**Aim 1.2: Multi-omics correlation analysis. Objective.** Genomics, transcriptomics and proteomics often have complementary roles to jointly perform a certain biological function and create a specific observable phenotype. Our objective in Aim 1.2 is to establish a correlation pattern between the multi-omics data and the outcome data in symptomatic COVID-19 patients. **Bioinformatics.** Multi-omics analyses will be performed on the first 300 samples to correlate outcome with cfDNA patterns, PBMC coding and non-coding mRNA expression, PBMC subpopulations and cytokine profiles (**Figure 2**). We will construct mixed effects regression models for each candidate feature. For continuous markers (cytokines) we will construct linear models. All logistic regression models will be stratified by primary composite outcome (single organ dysfunction, multiorgan dysfunction, and death). For count markers (sequencing), we will run negative binomial models. We will use the Benjamini-Hochberg procedure to control the FDR at alpha 0.05. If significant interaction effects are found after FDR adjustment, post hoc comparisons will be estimated using model contrasts and summarized with 95% confidence intervals estimated from the model. **Interpretation of Results.** Multi-omics correlations will add essential information in addition to the single omics analysis. We expect that the candidate genomic, transcriptomic, proteomic and clinical predictors will have distinct correlations within the two endpoint groups. This information can help characterize the biology of the immune response to COVID-19 and identify the most promising members for the prediction algorithm.

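### The Aim 2.1 cross-validated AUC and its gain over the clinical model are optimistic when weak markers pass the Aim 1 screen, because that screen used the same 300 patients and is not repeated inside the folds

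*Protocol*

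**What the plan says.** The Protocol sets out this sequence.

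- **Same patients.** Research Plan, Sample Size Requirements and Power Calculations: "Aim 2.1 training/testing of the predictive algorithm (n=300 from Aim 1.1".
- **Aim 1.1, staged screen.** "We will perform exploratory analyses on the first 100 samples and confirm these parameters on the following 200 samples". For transcripts the screen uses the endpoint: "Differentially expressed genes between positive and negative endpoint groups will be identified by non-parametric statistics (Mann-Whitney test with Benjamini-Hochberg correction". The threshold is: "We will use a more relaxed criteria of FDR=0.1 and fold change of at least 2.0 to identify significant genes".
- **Aim 1.2, screen on all 300.** "Multi-omics analyses will be performed on the first 300 samples to correlate outcome with cfDNA patterns" and the other omics layers, with this error control: "We will use the Benjamini-Hochberg procedure to control the FDR at alpha 0.05". No fold-change condition is given here.
- **Aim 2.1, models.** They "will be constructed using significant entities identified in the marker screening phase (Aim 1". Three logistic models (clinical, clinical plus omics, clinical plus a simplified omics list) are fitted by LASSO.
- **Aim 2.1, assessment.** "Ten-fold cross-validation will be used to estimate model performance in terms of AUC", and paired AUCs are compared by DeLong's test. The sample (60 with and 240 without the endpoint) is said to give 80% power for a delta AUC of 0.1, with correlation 0.5 and AUCs near 0.8.
- **Aim 2.2.** The comparison of the three models is to be validated in 200 patients who took no part in development.

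**The concern.** Cross-validation gives an honest AUC only if every step that looked at the outcome is redone without the held-out fold. Here only the LASSO step is described at the modelling stage. The marker list is already complete when the folds are drawn, and all 300 patients, including those in each held-out fold, contributed their outcomes to it. A marker that passed partly by chance will look predictive again in the fold that helped it pass.

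The tilt is uneven. Aim 1.1 also screens clinical parameters, so the clinical model may carry some optimism, but from far fewer candidates. The net effect favours the omics models.

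At stake are the AUC that Aim 2.1 reports, its DeLong p-value, and the conclusion the protocol expects there, that the multi-omics algorithm beats clinical data alone.

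**Working it through.** **1. The plan's own power figure.** Inputs from Aim 2.1: 60 positive, 240 negative, AUC A = 0.8, correlation r = 0.5, delta 0.1. Two-sided alpha 0.05 is an assumption; the protocol does not state it.

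Hanley-McNeil variance, with A/(2−A) = 0.6667, 2A²/(1+A) = 0.7111 and A² = 0.64:

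- Var = [0.8×0.2 + 59×(0.6667−0.64) + 239×(0.7111−0.64)] / (60×240) = 18.73/14,400 = 0.001301, so SE = 0.0361.
- SE of the paired difference = √(2 × 0.001301 × (1−0.5)) = 0.0361.
- Power = Φ(0.1/0.0361 − 1.96) = 0.792.
- Detectable delta at 80% power = (1.96 + 0.842) × 0.0361 = 0.101.

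The stated 80% reproduces. It presumes an unbiased AUC difference, which a screen run outside the folds does not guarantee.

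**2. Size of the bias, by simulation.** From the protocol: 60/240 patients, Mann-Whitney screen with Benjamini-Hochberg, LASSO, ten folds, DeLong's test, clinical AUC about 0.8. Assumed: number of features, number and strength of true markers, independent features, no fold-change filter. The true gain was measured in 2,000 fresh patients.

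| Scenario | Runs | Gain, screen outside folds | Gain, screen inside folds | True gain |
|---|---|---|---|---|
| A. 30 markers of 0.4 SD among 3,000; FDR 0.05 on all 300 | 60 | 0.058 | 0.018 | 0.021 |
| B. As A, FDR 0.10 on all 300 | 60 | 0.074 | 0.026 | 0.031 |
| C. 50 markers of 0.4 SD among 5,000; FDR 0.10 on all 300 | 20 | 0.109 | 0.043 | 0.050 |
| D. 20 markers of 0.8 SD among 3,000; FDR 0.10 in 100, then p<0.05 in 200 | 40 | 0.088 | 0.054 | 0.083 |
| E. No true marker among 5,000; FDR 0.10 on all 300, or staged | 20 each | nothing selected | nothing selected | 0 |

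A is the case closest to the text, since Aim 1.2 uses all 300 at FDR 0.05. Its mean bias was 0.038 (simulation SE 0.004), or 0.038/0.1 = 38% of the delta the plan is powered for. DeLong's test was significant in 70% of runs with the screen outside the folds and 23% with it inside. With 60 runs these carry about ±12 and ±11 points (1.96 × √(0.7×0.3/60) and 1.96 × √(0.23×0.77/60)). A separate simulation of weak markers at FDR 0.05 on all 300 gave 0.058 against 0.019.

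B and C show sensitivity only: they pair Aim 1.1's FDR level with Aim 1.2's sample. In D the mean bias was 0.005 (SE 0.004), not distinguishable from zero.

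**The case against.** **The independent cohort protects the claim.** This stands. Aim 2.2 compares clinical with clinical-plus-molecular models in 200 patients not used for development, with its own power statement. A reader might infer that the biased Aim 2.1 result decides which models go on to validation. The protocol contains no such gate: it names all three models and sends their comparison to Aim 2.2.

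**FDR control limits the damage.** This stands in part. A reader might infer that Aim 2.1 could report a large, significant gain from pure noise. That happens if a fixed number of top genes is always kept, which is not the protocol's rule. With no true marker, further runs with 10,000 genes passed none under the Aim 1.1 rule, and any gene in only about 5% of runs under FDR 0.05 on all 300. The bias arises when real but weak markers pass alongside chance.

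**The staged rule is strict.** This also stands in part. With 30 weak markers among 3,000, the 100-then-200 rule passed any gene in only 3–7% of runs. If Aim 1.2 tested only markers already confirmed in Aim 1.1, bias would be small. But the protocol does not say so, and Aim 2.1 draws on Aim 1 as a whole.

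**Not all of Aim 1 is supervised.** Correct. WGCNA module building is unsupervised; only the later linking of modules to outcome uses the endpoint.

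**Nesting may be set out in an analysis plan not shown.** Possible, and it would settle the point. The protocol, however, describes a finished marker list entering the models. Aim 2.1 also says that it largely follows the preliminary work, where the AUC rise from 0.69 to 0.90 was reported on 77 patients who included the 29 used for gene discovery.

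**Conclusion.** The concern holds for Aim 2.1. The overlap of patients, the outcome-driven screen and the lack of any nesting are all in the text, and the direction of the bias favours the omics models.

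The documents do not fix its size. Under scenario A the gain is overstated by about 0.04 (0.06 apparent, 0.02 true). Across the scenarios the bias ran from nothing, when no marker passes, through 0.005 with strong markers under a strict staged rule, to 0.109 − 0.050 = 0.059 in the most adverse case. All of this rests on assumed feature counts and signal strengths and omits the fold-change filter.

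The 80% power figure is not an arithmetical error. In scenarios A to C the true gain is positive, so the extra significant results are exaggerations, not false positives. The Aim 2.2 comparison is untouched. This should be fixed; it does not put the study's final claim at risk.

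**What to change.** 1. In Aim 2.1, state that the performance estimate repeats the whole supervised part of Aim 1 (the Aim 1.1 filter and confirmation, the Aim 1.2 marker models, and any choice of modules by outcome) and the LASSO penalty choice inside each of the ten training folds. The final algorithm is still fitted on all 300.
2. State that the Aim 2.1 DeLong comparison, with its 80% power for a delta AUC of 0.1, is descriptive, and that inference on the omics gain rests on the locked models in the 200 validation patients. The power statement need not be deleted.

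The cost is protocol wording, computing time and a less favourable Aim 2.1 AUC. Nesting can also err low: in scenario D it gave 0.054 against a true 0.083, because a staged screen within a fold has fewer patients. That is worth stating beside the result. No further patients or data are needed.
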